### **6.2 Genotyping**

If randomized to Arm 1 (genotyping arm), the research coordinator will obtain a buccal swab for the PGx test on the Spartan Rx system. If randomized to Arm 2 (control group), a saliva sample will be obtained with the Oragene-DNA 500 kit (DNA Genotek, Ottawa, Canada) and the genotyping will be performed at the completion of the study. For Arm 2, DNA will be extracted from saliva using the QIAamp DNA mini kit (Qiagen, Valencia, CA). Samples will be genotyped using the Infinium Global Screening Array (Illumina, SanDiego, CA), a genome-wide genotyping array that also contains pharmacogenetic variants. Genotyping will be performed on Illumina's iScan System at the Center for Advanced Genomics at the Children's Hospital of Philadelphia. The *CYP2C19* SNPs of interest \*2 (rs4244285), \*3 (rs4986893) and \*17 (rs12248560) will be extracted from the array data.

### **6.3 Clinical data collection**

Subjects in both arms will have baseline clinical data collected from medical records and will be telephoned every 3 months for clinical endpoint collection and medical service utilization. Medical records will be reviewed for the occurrence of major cardiac events (CV- related death, myocardial infarction, stroke, urgent need for revascularization, and stent thrombosis), bleeding events and death until May 31, 2017.

### **6.4 Health-related quality of life (HrQoL)**

Subjects in both arms will complete a baseline SF-12 and 4 additional questionnaires by phone or on paper and returned by mail (every 3 months).

### **6.5 Patient attitudes towards pharmacogenetic testing**

Patients will complete a paper survey at 3 months to assess their understanding and attitudes towards pharmacogenetic testing (Appendix B).

### **6.6 Provider attitudes towards pharmacogenetic testing**

Treating physicians participating in the study will complete a survey at baseline and 1 year to assess their attitudes towards pharmacogenetic testing and needs for medical education in this area (Appendix C).

### **6.7 Collection of saliva for future genetic tests**

An optional component of the study will be saliva collection for DNA biobanking. If the subject provides consent for this component, a saliva sample will be collected with the Oragene-DNA 500 kit (DNA Genotek. This is the same sample we are collecting in 6.2 above for the control group and not a separate sample. To avoid confusion for subjects and study personnel, a saliva sample will be collected for all participants and the purpose will be labeled (e.g. for *CYP2C19* genotyping only OR for biobanking and *CYP2C19* genotyping).

## 7.0 STATISTICAL ANALYSIS

Data collected in this study will be reported using summary tables and results will be displayed for each treatment arm. For categorical variables, frequencies and percentages will be presented. For continuous variables, the number of subjects, mean, standard deviation, minimum, 25th percentile, median, 75th percentile and maximum will be presented. Reported differences will include standard errors and 95% CI. Analyses will be based on the intention to treat. Continuous variables will be compared using Student's t-test. Categorical variables will be compared using the chi-square test or Fisher's exact test when appropriate.

### 7.1 Primary endpoints

1. We will tabulate the number and proportion of prasugrel/ticagrelor in each Arm. We will compare discharge antiplatelet therapy choice between the genotype and control arm using the chi-square or Fisher's exact test. The probability of receipt of antiplatelet agents will be determined by logistic regression.

### 7.2 Secondary endpoints

1. Implementation.
  - a. We will estimate adherence to suggested treatment recommendations based on results of the *CYP2C19* genetic test. The adherence rate is defined as the number of participants in Arm 1 with LOF variants that received prasugrel or ticagrelor + the number of participants without these variants that received clopidogrel divided by the total number in Arm 1.
  - b. We will tabulate reasons for non-adherence to recommendations.
2. Clinical outcomes.
  - a. Frequencies of CV related death, MI, stroke urgent, need for revascularization and stent thrombosis will be reported as will frequencies of bleeding complications. We will determine time to first major cardiac event as a composite endpoint (CV related death, MI, stroke urgent need for revascularization and stent thrombosis). The incidence of first MACE and first major bleeding events between the groups will be compared by use of Kaplan-Meier estimators and statistical tests will be evaluated based on log-rank tests.
  - b. To determine whether MACE outcomes differ in participants with ACS, an interaction term between ACS and group assignment will be tested in a Cox proportional hazard model.
3. Medical service utilization. We will develop descriptive statistics for use of antiplatelet drugs, use of other cardiovascular medications, number of hospitalizations, number of physician visits, and use of rehabilitation services
4. Direct medical cost. We will also develop descriptive statistics for total cost, *CYP2C19* genetic testing cost, medication cost, hospitalization cost, physician visit cost, and rehabilitation cost.
5. Preference scores / QALYs. We will develop descriptive statistics for the SF-12 physical and mental scale scores, the SF-6D, a preference-based health-related quality of life score that can be derived from the SF-12, and for QALYs, a composite measure of its quality (based on the SF-6D). We will also report the correlation between the difference in cost and difference in QALYs (this correlation will be used in sample size estimation for the full study that this pilot study is designed to support).
6. Incremental cost-effectiveness ratio. Based on the differences in primary outcomes total cost and QALYs, we will calculate the ratio incremental costs divided by incremental QALYs, the 95% CI for this ratio, and the cost-effectiveness acceptability curve.

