#### 4.3 Tertiary Endpoints

- a. Additional implementation metrics
  - a. Number of genotype results returned
  - b. Average genotype test completion time
  - c. Genotype assay failure rate (inconclusive test result)
  - d. Number/reason for screening failure
  - e. Time from test order to result in medical record
- b. Patient attitudes towards PGx testing as determined by questionnaire will be completed at the 3 month phone follow-up.
- c. Prescriber attitudes towards PGx testing as determined by questionnaire that will be administered at the start and end of the study.

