**Table 1. Treatment recommendations for antiplatelet therapy based on CYP2C19 genotype**

Genotype	Phenotype	Description	Treatment a
CYP2C19 *1/*1	Extensive metabolizer (normal)	Two inferred normal alleles	Clopidogrel 75 mg per day
CYP2C19 *1/*17	Ultra-rapid metabolizer	One inferred normal allele One increased function allele	
CYP2C19 *17/*17		Two gain of function alleles	
CYP2C19 *1/*2	Intermediate metabolizer	One inferred normal allele One loss of function allele	Prasugrel (Effient) 10 mg per day b Or Ticagrelor (Brilinta) 90 mg twice daily c
CYP2C19 *1/*3		One inferred normal allele One loss of function allele	
CYP2C19 *2/*17		One loss of function allele One gain of function allele	
CYP2C19 *3/*17		One loss of function allele One gain of function allele	
CYP2C19 *2/*2	Poor metabolizer	Two loss of function alleles	Prasugrel (Effient) 10 mg per day b Or Ticagrelor (Brilinta) 90 mg twice daily c
CYP2C19 *3/*3		Two loss of function alleles	
CYP2C19 *2/*3		Two loss of function alleles	

a Please consider all clinical contraindications before prescribing alternative antiplatelet agent.

Prasugrel and ticagrelor are recommended only when not clinically contraindicated.

b Consider prasugrel 5 mg per day for patients <60 kg.

Individual risks/benefits of prasugrel must be carefully considered in patients over age 75.

Do not use prasugrel in patients with active bleeding or a history of transient ischemic attack or stroke.

Do not start prasugrel in patients likely to undergo **urgent** coronary bypass graft surgery (CABG).

c Do not use ticagrelor in patients with active bleeding or a history of transient ischemic attack or stroke.

Do not start ticagrelor in patients likely to undergo **urgent** coronary bypass graft surgery (CABG).

Do not use maintenance aspirin doses above 100 mg in combination with ticagrelor.

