## Section 4: Statistical Principles

Section/Item	Index	Description
Confidence intervals and p-value	16	The primary outcome was claimed at an alpha level of $p=0.05$ .
	17	No corrections were made for multiple testing.
	18	Confidence intervals pertaining to the probability of receipt of antiplatelet agents were reported.
Adherence and protocol deviations	19a	Adherence to the genotype guided recommendations was assessed in the genotyped group by comparing the discharge antiplatelet medication to those recommended by the CPIC guidelines. The research coordinator asked the prescribing cardiologists to provide any reasons for non-adherence. Adherence was not described in the usual care group as prescribing decisions were made by the cardiologist as per usual care.
	19b	The adherence rate was defined as the number of participants in genotyped group with LOF variants that received prasugrel or ticagrelor + the number of participants without these variants that received clopidogrel divided by the total number in this group
	19c	The only protocol deviations that were encountered in this trial were enrollment of participants that did not meet the inclusion/exclusion criteria. Since this was a pragmatic clinical trial, most of the procedures were performed within the context of usual care.
	19d	Participants that did not meet inclusion/exclusion criteria and were withdrawn from the study by the treating physician or study staff.
Analysis population	20	Modified intent to treat (removing the participants that did not meet the inclusion criteria).

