## Section 6: Analysis

Section/Item	Index	Description
Outcome definitions	26a	
Primary outcome: The number and proportion of participants receiving prasugrel/ticagrelor at discharge from index PCI in each randomized. Timing <7 days
 
Secondary Outcomes:
 
 
1. Adherence to the CPIC guideline suggested antiplatelet therapy recommendations based on genotype (intervention group only). Timing <7 days.
 
2. Major adverse cardiac events (MACE) defined as cardiovascular death, myocardial infarction, stroke, urgent need for revascularization, and stent thrombosis (Academic Research Consortium “definite” stent thrombosis). Timing at last follow-up.
 
3. Major bleeding events as defined by the Bleeding Academic Research Consortium (BARC) type 3 or 5. Timing at last follow-up.
 
4. Non-cardiac mortality. Timing at last follow-up.
 
5. Implementation Metrics. Timing < 7days 
 
a. Genotype test turnaround time (Time result reported to physician – time of buccal swab).
 
b. Number of inconclusive results.
 
 
 

	26b	n/a
	26c	Time to MACE or major bleed

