Analysis methods	27a	
Primary outcome: Discharge antiplatelet therapy choice by genotyped and usual care group was compared using the chi-square or Fisher's exact test. The probability of receipt of antiplatelet agents was determined by logistic regression.
 
Secondary outcomes:
 
 
1. The adherence rate to the genotype guided recommendations for the genotyped group was determined by reporting the number of participants with LOF variants that received prasugrel or ticagrelor + the number of participants without these variants that received clopidogrel divided by the total number in the genotyped arm.
 
2. Clinical outcomes. Frequencies of CV related death, MI, stroke urgent, need for revascularization and stent thrombosis was reported as well frequencies of bleeding complications and compared using chi-square test or Fisher's exact test when appropriate. The time to first major cardiac event as a composite endpoint (CV related death, MI, stroke urgent need for revascularization and stent thrombosis) was determined. The incidence of first MACE and first major bleeding events between the groups was compared by use of Kaplan-Meier estimators and statistical tests evaluated based on log-rank tests.
 
3. Implementation. The turnaround time for test result in the
 

		genotyped group was presented as mean ± standard deviation (hours).
27b	n/a	
27c	n/a	
27d	n/a	
27e	n/a	
27f		To evaluate whether genotyping influenced MACE outcomes in participants with ACS, an interaction term between ACS and group assignment was tested in a Cox proportional hazard model.
Missing data	28	For time to MACE analysis, participants were censored at the date of event or time of known last follow-up.

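### The physician adherence rate divides by all of Arm 1, including participants whose physician had no genotype result

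*Protocol*

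**What the plan says.** The adherence rate appears three times with the same structure.

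- Protocol 7.2, item 1a, adds the "number of participants in Arm 1 with LOF variants that received prasugrel or ticagrelor" to "the number of participants without these variants that received clopidogrel", and the sum is "divided by the total number in Arm 1".
- SAP item 19b ends "divided by the total number in this group", meaning the genotyped group.
- SAP item 27a ends "divided by the total number in the genotyped arm".

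The protocol synopsis gives the same numerator but does not say which total it divides by.

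Both documents expect some tests to give no usable answer. Protocol 4.3 lists the number of results returned and the assay failure rate as tertiary endpoints. SAP item 26a lists "Number of inconclusive results" as an implementation metric. Neither says how these participants enter the adherence rate. The SAP's modified intention-to-treat population (item 20) removes only participants who did not meet the entry criteria, so those without a result remain.

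The target of the endpoint is clear. The synopsis lists physician adherence to the genotype-guided recommendations as a secondary objective. The protocol introduction and the SAP background ask whether physicians follow such recommendations once they are shown the results.

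Table 1 of the protocol adds a condition: "Prasugrel and ticagrelor are recommended only when not clinically contraindicated".

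**The concern.** The numerator and denominator cover different people. To enter the numerator, a participant must be classed as a carrier or a non-carrier and have received the matching drug. To enter the denominator, it is enough to have been randomised to Arm 1 and to be eligible. Someone with an inconclusive test counts only in the denominator, although there was no recommendation for the physician to follow or to depart from.

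This matters for the pilot's stated use. The protocol introduction says that implementation metrics will help to estimate how far testing would penetrate in a later trial. A planner who multiplies the share of results returned by the reported adherence rate would count assay failure twice.

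Pooling raises a related problem. Most participants are non-carriers, and clopidogrel was already the usual choice. Much of the pooled rate can therefore arise without any response to the test.

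**Working it through.** **The plan's own figure.** The only related figure that can be reproduced is the sample size. With 35% versus 20%, two-sided alpha 0.05, 80% power, pooled variance under the null and no continuity correction:

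n = [1.960 × √(2 × 0.275 × 0.725) + 0.842 × √(0.35 × 0.65 + 0.20 × 0.80)]² / 0.15² = 138 per group.

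This matches the documents and does not depend on how adherence is defined.

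**Inputs for adherence**

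- From the sample size sections: about 250 per arm, 30-35% loss-of-function carriers, 20% pre-study prasugrel/ticagrelor use.
- Assumed, because the documents give neither: adherence A = 80% among returned results, and a no-result share f of 2%, 5% or 10%.

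**1. The rule as written.** Participants without a result add nothing to the numerator, so the reported rate is A × (1 − f).

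| f | Participants of 250 | Reported rate |
|---|---|---|
| 2% | 5 | 0.80 × 0.98 = 78.4% |
| 5% | 12.5 | 0.80 × 0.95 = 76.0% |
| 10% | 25 | 0.80 × 0.90 = 72.0% |

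**2. Two other readings, at f = 5%**

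- *Typed later.* Protocol 6.7 collects saliva from all participants, so a failed swab might be typed afterwards. Take 32.5% carriers and prescribing at the 20% pre-study rate. The share that matches by chance is 0.675 × 0.80 + 0.325 × 0.20 = 60.5%. The rate becomes 0.95 × 0.80 + 0.05 × 0.605 = 79.0%.
- *Treated as non-carriers.* If those with no result are classed as having no variant and 80% receive clopidogrel, the rate is 0.95 × 0.80 + 0.05 × 0.80 = 80.0%.

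Both readings score physicians against a recommendation that was never issued.

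**3. Double counting by a later planner, at f = 5%.** The share of participants tested and treated as recommended is 0.95 × 0.80 = 76%. Multiplying the returned share by the reported rate gives 0.95 × 0.76 = 72%.

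**4. Pooled rate if prescribing ignored genotype**

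- 30% carriers: 0.70 × 0.80 + 0.30 × 0.20 = 62%.
- 35% carriers: 0.65 × 0.80 + 0.35 × 0.20 = 59%.

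The separate rates would be 80% in non-carriers and 20% in carriers, which shows the lack of response at once.

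**5. Carriers with a contraindication.** If a share e of carriers could receive neither drug, full compliance would give at most 1 − q × e, where q is the carrier share. With e assumed to be 10%, the ceiling is 1 − 0.30 × 0.10 = 97.0% or 1 − 0.35 × 0.10 = 96.5%.

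**The case against.** **The whole-arm denominator can be defended.** The endpoint is filed under implementation, the trial is pragmatic and the analysis is by intention to treat. A whole-arm rate answers a fair question: what share of those sent for testing ended up treated in line with their genotype? That is a good reason to keep the rate as supportive. It does not make it a measure of physician adherence, which is the objective the documents state.

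**The parts are reported elsewhere.** Results returned, inconclusive results and reasons for non-adherence are all tabulated, so a reader could largely rebuild the other rate. This lessens the harm, but the headline figure stays as defined.

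**The size is unproved.** This stands. At 80% and 250 participants, the 95% confidence half-width is 1.96 × √(0.80 × 0.20 / 250) = 5.0 points. The shifts at 2% and 5% without a result (1.6 and 4 points) lie inside it. However, the shift is systematic and would not shrink with more participants.

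**Two stronger readings that a reader might infer.** The first is that every participant without a result must be scored as non-adherent, so that adherence is understated by a known factor. The literal formula does this, but the documents do not say which assay defines carrier status, and the alternatives above give 79.0% or 80.0% instead of 76%. The second is that carriers excused by the Table 1 footnote depress the rate materially. The documents do not support that. Exclusions 1 to 3 substantially cover the contraindications listed for both drugs (active bleeding, prior TIA or stroke, likely urgent bypass surgery). The remaining listed cautions each concern one drug, and receiving either drug counts as adherent. What is left is unlisted contraindications, coinciding cautions, or events after enrolment, which are probably few.

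**Conclusion.** The point holds. All three full definitions use a denominator that includes participants whose physician had no result, and nothing in either document removes them. Followed as written, the rule gives a rate that mixes test performance with prescriber behaviour.

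The size is unknown. At an assumed 80% adherence, the literal rule lowers the rate by 1.6 to 8 points for 2-10% without a result, and by less or not at all under the other readings. The case for splitting carriers from non-carriers is firmer: the 59-62% score for genotype-blind prescribing uses the plan's own inputs and assumes only that the pre-study rate applies equally to both groups. The contraindication condition is a minor matter of presentation.

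This is a descriptive, single-arm secondary endpoint without a test or threshold. The primary comparison and the 138 per group are untouched.

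**What to change.** In protocol 7.2 and SAP items 19b and 27a:

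1. Define the main adherence rate among Arm 1 participants with a conclusive result reported to the physician, before discharge where timing allows. SAP item 26a uses the time of reporting, but neither document lists a prescribing time. If none was recorded, use all conclusive reported results and say so.
2. Give the number and share of Arm 1 without such a result beside that rate, and state that genotypes obtained later do not enter it.
3. Keep the all-Arm-1 rate as supportive, and state how it treats participants without a result.
4. Report adherence separately for carriers and non-carriers, with confidence intervals.
5. In the table of reasons for non-adherence, show a stated contraindication as its own category. No contraindication field is listed and cardiologists were only asked for their reasons, so this should stay descriptive.

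The cost is a change of wording, a slightly smaller denominator and one more table. Items 2 to 5 use data that the plan already collects, and item 1 depends on what timing was recorded. No treatment recommendation changes.

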Study Design	
The study utilizes a novel genotyping device, SpartanRx™ (Spartan Bioscience, Ottawa, Canada) that provides identification of a patient's CYP2C19 *2, *3, and *17 genotypes determined from genomic DNA from a buccal swab sample with 1 hour turnaround time.
 
PCI Patient Study
 
This is a randomized, prospective, pragmatic open label study. Patients undergoing percutaneous intervention (PCI) with stent implantation, who require anti-platelet therapy, will be randomized either to: Arm 1) genotype guided dosing of antiplatelet therapy or Arm 2) usual care.
 
In Arm 1, a buccal swab will be obtained from subjects immediately following PCI/stent, to determine CYP2C19 genotype with the SpartanRx system. Subject with slow metabolizer status [1 or 2 loss-of-function (LOF) mutations (*2 or *3) in CYP2C19] will be recommended to initiate therapy with prasugrel or ticagrelor in place of clopidogrel. Subjects with normal metabolizer status (homozygous for the *1 allele in CYP2C19) will be recommended to initiate therapy with clopidogrel. Antiplatelet choice is ultimately decided by physician judgment incorporating all clinical factors.
 
In Arm 2, choice of antiplatelet therapy will be decided by treating physician as per usual care. DNA will be collected via a saliva sample to assess CYP2C19 genotype at the conclusion of the study.
 
Subjects in both groups will complete a baseline health related quality of life questionnaire (HrQoL) and additional clinical data pertaining to cardiac history will be collected from medical records. Subjects will be contacted every three months for medical services utilization, clinical information, and HrQoL assessments for a total of one year. Medical records will be reviewed for clinical outcomes until May 31, 2017.

Study Duration	3 years
Study Centers	Hospital of the University of Pennsylvania (HUP) Penn Presbyterian Medical Center (PPMC)
Primary Objective	To determine the effect of CYP2C19 genotyping on the prescribing of antiplatelet therapies following PCI.

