#### 4.2 Secondary endpoints

1. Implementation
  - a. Adherence to suggested treatment recommendations based on genotype
  - b. Reasons for non-adherence to recommendations Medical service utilization
2. Clinical Outcomes
  - a. Major adverse cardiac event (CV related death, MI, stroke, urgent need for revascularization, stent thrombosis, all deaths).
  - b. Bleeding complications (defined by the Bleeding Academic Research Consortium).
  - c. Clinical outcomes will be ascertained by medical records until May 31, 2017.
3. Economic- Incremental cost effectiveness ratio per quality adjusted life-year (ICER/QALYs).
  - a. Medical services utilization
  - b. Cost of services
  - c. Preference score (SF-12 questionnaire) performed at baseline and every 3 months for one year for determination of QALYs.

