## **6.0 STUDY PROCEDURES**

### **6.1 Informed Consent**

Subjects will be approached for enrollment 2 hours following their PCI/stent implantation in the holding area or their inpatient hospital bed by the research coordinator.

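### Incremental QALYs and the ICER are planned from between-arm differences with no baseline SF-6D adjustment named; adjusting could gain precision, mainly on QALYs, provided the baseline SF-12 precedes knowledge of the arm

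*Protocol*

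**What the plan says.** Item 6 of Protocol 7.2 covers the ICER, its 95% CI and the acceptability curve: "Based on the differences in primary outcomes total cost and QALYs, we will calculate the ratio incremental costs divided by incremental QALYs". It names no covariate and no regression.

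Items 4 and 5 are descriptive. For cost: "We will also develop descriptive statistics for total cost". For SF-6D and QALYs, item 5 plans summaries and the correlation between the cost and QALY differences, and adds that "this correlation will be used in sample size estimation for the full study that this pilot study is designed to support".

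The general rule in Protocol 7.0 is "Continuous variables will be compared using Student's t-test". The protocol's only covariate list belongs to the post-hoc Cox models of clinical events (7.4). The SAP has no cost, QALY or ICER analysis in its objectives (item 8), outcome definitions (item 26a) or methods (item 27a).

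The covariate is already scheduled. Protocol 4.2 lists "Preference score (SF-12 questionnaire) performed at baseline and every 3 months for one year for determination of QALYs", and 6.4 says "Subjects in both arms will complete a baseline SF-12 and 4 additional questionnaires by phone or on paper".

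On timing, 6.1 says "Subjects will be approached for enrollment 2 hours following their PCI/stent implantation", and the Synopsis says "This is a randomized, prospective, pragmatic open label study". Neither document says whether the baseline SF-12 comes before or after allocation.

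**The concern.** If QALYs are computed as an area under the SF-6D curve, the baseline score is part of the outcome and probably also correlates with later scores. A chance baseline imbalance then passes into the incremental QALYs, and variation that baseline could explain stays in the standard error. Baseline adjustment removes both at almost no cost when the score is already collected.

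At stake is the width of the interval for incremental QALYs and, to a lesser degree, of the ICER interval and acceptability curve. There is also a small planning effect. A later trial that adjusts for baseline would need the adjusted QALY variance and cost-QALY correlation, and item 5 does not list these among its outputs.

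**Working it through.** **Plan's own figures.** The documents give no SD, precision or power figure for QALYs or the ICER. The nearest figure is row 2 of Table 2 in Protocol 7.6 (hospital cost, mean 7,800, SD 9,355, 350 per arm). A log-normal simulation with 20,000 runs gives 6,873 to 8,847 for the mean (stated: 6,851 to 8,775) and 6,798 to 13,383 for the SD (stated: 6,875 to 13,138). This agrees apart from simulation noise.

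**Inputs from the documents.** Five SF-12 assessments (4.2, 6.4); 250 per arm (7.5) or 350 per arm (7.6); hospital-cost SDs of 9,355 and, in the most extreme case, 18,000 (7.6).

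**Assumptions.** Trapezoid QALY over one year; complete data; no deaths; SF-6D SD of 0.13 at each visit; the visit correlations below; $50,000 or $100,000 per QALY; hospital-cost SD standing in for total-cost SD.

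**Step 1: QALY difference.** The trapezoid weights are 1/8, 1/4, 1/4, 1/4, 1/8, so the four later visits carry 7/8. In units of the SF-6D variance, let c be the covariance of baseline with the QALY (also the regression slope) and v the QALY variance. Adjustment cuts the variance by r² = c²/v.

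Example with equal correlation 0.7: c = 0.125 + 0.875 × 0.7 = 0.7375. The later visits contribute 0.203125 + 0.7 × (0.765625 − 0.203125) = 0.596875. So v = 0.015625 + 2 × 0.125 × 0.875 × 0.7 + 0.596875 = 0.765625, and r² = 0.5439/0.7656 = 71.0%.

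| Assumed correlations | c | v | Variance cut r² |
|---|---|---|---|
| Baseline 0.1 with later visits, later visits 0.7 with each other | 0.2125 | 0.6344 | 7.1% |
| Same, baseline 0.2 | 0.3000 | 0.6562 | 13.7% |
| Same, baseline 0.3 | 0.3875 | 0.6781 | 22.1% |
| Decaying, 0.3 per visit | 0.2303 | 0.3574 | 14.8% |
| Decaying, 0.5 | 0.3516 | 0.4863 | 25.4% |
| Decaying, 0.7 | 0.5383 | 0.6541 | 44.3% |
| Equal, 0.4 | 0.4750 | 0.5312 | 42.5% |
| Equal, 0.7 | 0.7375 | 0.7656 | 71.0% |

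Simulation (4,000 trials per setting, 250 per arm) gave cuts of 43.1% and 70.8% for equal 0.4 and 0.7. Both estimators averaged within 0.0002 of zero, so neither is biased.

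The SE is 0.13 × √v × √(2/n), times √(1 − r²) after adjustment. With 250 per arm it goes from 0.0093 to 0.0089 in the first row and from 0.0102 to 0.0055 in the last. With 350 per arm it goes from 0.0078 to 0.0075 and from 0.0086 to 0.0046.

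**Step 2: net benefit.** Write L = threshold × QALY SD, S = cost SD and ρ = cost-QALY correlation, with cost correlating with baseline at ρr. The net-benefit variance is L² + S² − 2ρLS. With baseline in both equations, the proportion removed is r²(L − ρS)²/(L² + S² − 2ρLS).

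- ρ = 0, $50,000. The first row has L = 5,177 and the last row L = 5,688. The cut is 1.7% to 19.2% with S = 9,355 and 0.5% to 6.4% with S = 18,000.
- ρ = −0.3, S = 9,355, last row: 0.7104 × (5,688 + 2,807)² / (32.3 + 87.5 + 31.9 million) = 34%.
- ρ = +0.3, S = 18,000, last row: L − ρS = 5,688 − 5,400 = 288, so the cut is about 0.02%. It is about 0% in every row.
- ρ = 0, $100,000: L doubles, and the cut is 3.9% to 42.4% (S = 9,355) or 1.8% to 20.3% (S = 18,000).

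If only QALYs are adjusted, the proportion removed is r²(L² − 2ρLS)/(L² + S² − 2ρLS). At $50,000 and ρ from −0.3 to +0.3, this runs from a 30% cut to a 2% rise (S = 9,355), or from a 16% cut to a 7% rise (S = 18,000). The covariate therefore belongs in both equations.

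**Step 3: timing.** Suppose knowing the arm shifted one arm's baseline score by an assumed 0.02 and nothing else. The unadjusted bias is 0.02/8 = +0.0025. The adjusted bias is 0.02 × (0.125 − c), which runs from −0.002 (c = 0.2125) to −0.012 (c = 0.7375).

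**The case against.** The strongest case against is that nothing here is wrong. An adjusted difference is still a between-arm difference, so item 6 leaves the estimator open and does not rule adjustment out. The economic aim is a pilot. Section 7.6 promises only precision for hospital-cost means and SDs, and participant-level data can be exported (8.0), so adjusted quantities can be computed later. All of this stands, and it keeps the point minor.

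The size is also soft. A baseline score taken soon after PCI may predict later scores weakly, which is why the range starts at 7%. Deaths, an endpoint in 4.2, would add QALY variance that baseline may not explain. Total cost may vary more than hospital cost, shrinking the net-benefit gain further. These objections stand too.

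A reader might infer more than the documents support, in three ways:

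- **That the unadjusted ICER is biased or its interval invalid.** Under randomization it is neither.
- **That the t-test rule shows an unadjusted estimator was chosen.** It is a general rule, and a t-test cannot supply an interval for a ratio or an acceptability curve.
- **That the trial's primary result is touched, because item 6 calls cost and QALYs primary outcomes.** Section 4.1 makes prescribing the primary endpoint, and 4.2 lists the economic measures as secondary.

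What survives is that a covariate already scheduled in both arms is left unused in the written plan, and that naming the estimator beforehand prevents a choice after the results are seen.

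**Conclusion.** The point holds as a conditional gain in precision, mainly on QALYs. Under the stated assumptions, adjustment cuts the variance of the QALY difference by about 7% to 71%. On the net-benefit scale at $50,000 per QALY the cut is between about 0% and about a third, so a narrower ICER interval cannot be promised. The documents give none of the SF-6D SD, visit correlations, QALY rule, threshold or total-cost SD, so the ranges illustrate and do not predict.

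The gain also depends on the baseline SF-12 being completed before the arm is known, which neither document states. It might be tempting to conclude that the baseline scores are contaminated. The documents do not show that; they only leave the order open.

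Severity is minor. No power claim and no primary conclusion changes.

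**What to change.** - **Item 6.** Estimate incremental QALYs by regression on arm and baseline SF-6D, and put the same covariate in the cost equation. Bootstrap the two regressions jointly for the ICER interval and acceptability curve. The randomization strata (ACS in Protocol 4.0; ACS and hospital site in SAP item 10) may be added, but no gain is claimed for them.
- **Timing.** State that the baseline SF-12 is completed before the arm is known. If that cannot be shown, keep the unadjusted difference as the main result and report the adjusted one as a sensitivity analysis.
- **Missing baseline scores.** Impute them without using arm, and use the imputed value both as the covariate and in the QALY calculation.
- **Item 5.** Report the QALY variance and the cost-QALY correlation both unadjusted and baseline-adjusted.

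The cost is a little more analysis and some protocol wording, with no added visits or participants. If the baseline SF-12 is not already completed before allocation, the order of baseline procedures would have to be set.
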